Appendix B: Sample SAS® code for analyses of efficacy endpoints for example SAS code.

Each of the complete datasets after imputation will then be analyzed in an analysis of covariance (ANCOVA) model adjusting for treatment and for randomization stratification factors, i.e. T2DM status (T2DM patients versus non-T2DM patients) and NASH CRN fibrosis scoring system (F1 versus F2/F3), and for the baseline LFC as a continuous covariate in the ITTS. Results from each complete dataset will be combined using Rubin's rule to provide the least square means (LSMs) for treatment groups at Week 36, standard error of the LSM, pairwise differences (PXL065 7.5 mg QD, 15 mg QD and 22.5 mg QD versus placebo) in LSMs, p-values and 95% CIs, see

Appendix B: Sample SAS® code for analyses of efficacy endpoints for example SAS code.

The ANCOVA model validity will be checked using appropriate plots (studentized residuals vs predicted values, etc.).

In addition, descriptive statistics on the non-imputed LFC and percentage changes from baseline will be calculated by visit within each treatment group.

Statistical Analysis Plan

Sponsor Name: Poxel
Sponsor Protocol ID: PXL065-003

A listing of LFC data will be produced for the ITT set with site 065-S .

7.6.1.2 Sensitivity Analysis for the Primary Analysis

The imputation method described in the primary analysis will be repeated and each of the complete datasets after imputation will then be analyzed with non-parametric pairwise Wilcoxon tests stratified according to T2DM status and NASH CRN fibrosis scoring system. Hodges-Lehmann midpoint estimates along with their 95% confidence intervals will also be provided for the ITTS for each imputed data set and then combined using Rubin's rule, see Appendix C for example SAS code.

7.6.1.3 Other Analyses for the Primary Endpoint

The same statistical analyses described in Sections 7.6.1.1 and 7.6.1.2 will be repeated for the ITTS-w-065-S .

Additionally, analyses described in Sections 7.6.1.1 and 7.6.1.2 will be repeated without the multivariate imputation on missing Week 36 data for the ITTS and the PPS.

7.6.1.4 Subgroup Analysis

Subgroup analyses will be performed for the primary endpoint for the following subgroups:

- Baseline age group (<65 years, \geq 65 years) ;
- Baseline BMI (<median, \geq median);
- Sex (female and male);
- Randomization strata of T2DM status (T2DM patients, non-T2DM patients);
- Randomization strata of NASH CRN fibrosis scoring system (F1, F2/F3);
- Baseline LFC (<median, \geq median);
- Site pooling. (Investigators specialty [Hepatology, Other]);

For each subgroup, the LSM differences and the 90% CI will be presented. The subgroup by treatment interaction will be tested at the nominal alpha level of 0.1. The subgroup analysis will be performed on the ITTS.

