#### Primary analysis:

The primary endpoint, i.e. expressed as the relative change in the percentage of LFC (assessed by MRI-PDFF) from baseline to Week 36 (V8-EoT), will be analyzed in an analysis of covariance (ANCOVA) model adjusting for treatment (PXL065 doses of 7.5 mg QD, 15 mg QD and 22.5 mg QD and placebo) and for stratification factors, i.e. T2DM status (T2DM patients versus non-T2DM patients) and NASH CRN fibrosis scoring system (F1 versus F2/F3), and for the baseline LFC as a continuous covariate.

The LSMs of the primary endpoint for treatment groups and pairwise differences in LSMs will be estimated along with p-values and 95% confidence intervals.

The validity of the ANCOVA model will be checked (studentized residuals will be plotted against predicted values, etc.).

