#### Subgroup analyses:

Subgroup of interest will be analyzed for the primary endpoint.

Subgroup analyses will be displayed with a forest plot to check consistency of the treatment effect across subgroups. Tests for subgroup by treatment interaction at the nominal alpha level of 0.10 will be provided and further detailed in the SAP:

- baseline age group (<65 years,  $\geq$ 65 years)
- BMI (<median and  $\geq$  median)
- Sex (female and male)

- T2DM status (T2DM patients versus non-T2DM patients)
- NASH CRN fibrosis scoring system (F1 versus F2/F3)
- Baseline LFC (assessed by MRI-PDFF) (<median and  $\geq$  median)
- Pooling site. Before unblinding, the rule of pooling site according to geographical area or other rationale shall be discussed by study team and documented in SAP.

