5.9 Per-Protocol Set (PPS)

The PPS consists of all ITTS-w-065-S patients without any important deviation of study procedures some of which include but are not limited to the following:

- Inclusion/Exclusion criteria likely to affect the primary efficacy endpoint satisfied
- Absence of relevant protocol violations with respect to factors likely to affect the primary efficacy endpoint where the nature of protocol violation will be defined before breaking the blind
- Adequate study medication compliance (80-120%) for the overall treatment period where patient has passed Week 12.
- Adequate measurement of the primary variable

The above criteria for the PPS are described in further detail in Section 5.10. Important protocol deviations (PDs) will be identified prior to breaking the blind. All important protocol deviations will be assessed for exclusion from the PPS during the blinded data review meeting (BDRM).

Patients in the PPS will be analyzed based on treatment actually received and actual strata rather than randomized.

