7.2 Patient Disposition and Data Sets Analyzed

Patient disposition will be listed and summarized (for screened set and screened set with site 065-S) by treatment group and overall and will include the number and percentage of patients:

- Screened;
 - Discontinued during screening period;
 - Discontinued during screening period due to COVID-19
- Randomized into double-blind period
 - Randomized but did not receive a dose of IMP
 - Randomized and received at least one dose of IMP;
 - Randomized but discontinued IMP/Study;
 - Patients whose primary reason for withdrawal was due to COVID-19 pandemic circumstances;
 - Patients who had study treatment temporarily interrupted due to COVID-19 pandemic circumstances
 - Randomized but not completed due to Site Early Termination;
 - Completed double-blind period
 - Patients who had study treatment temporarily interrupted due to COVID-19 pandemic circumstances
- Entered into follow-up period

Statistical Analysis Plan

Sponsor Name: Poxel
Sponsor Protocol ID: PXL065-003

- Discontinued during follow-up period;
 - Patients whose primary reason for withdrawal was due to COVID-19
- Completed follow-up period

In addition, the number and percentage of patients who discontinue early, including a breakdown of the primary reasons for discontinuation from study, will be presented.

A summary of the reasons for screen failure will be produced.

A summary table of randomized patients by site and treatment group will be provided for the randomized set.

A summary table of patients included in each study population (RS, Safety, ITT, PPS) will be produced for the Randomized set and Randomized set with site 065-S . A listing of patients included from each population will be produced, for the Randomized set with site 065-S: .

In addition, a summary table and listing will be produced for discrepancies between the stratification factors in the database and Interactive Web Response System (IWRS).

A listing of IMP kit numbers and assignments will be produced for the Randomized set with site 065-S: .

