7.4 Demographics and Other Baseline Characteristics

Demographic and baseline characteristics will be listed for the ITTS-w-065-S and summarized by treatment group and overall for the ITTS. Standard descriptive statistics will be presented for:

- Sex;
- Race (American Indian or Alaska Native, Asian, African American, Native Hawaiian or Other Pacific Islander, White, Other);
- Ethnicity (Hispanic or Latino, Not Hispanic or Latino, not stated, unknown);
- Age (years) at screening (derived on eCRF);
- Age group (years) at screening (<65 years, ≥ 65 years) ;
- Height (cm) at screening visit;
- Weight (kg) at baseline;
- Body mass index (BMI) (kg/m²) (derived on eCRF) at baseline;
- BMI (<median, ≥ median) at baseline;

Statistical Analysis Plan

Sponsor Name: Poxel
Sponsor Protocol ID: PXL065-003

- Child-bearing potential (yes, no, not applicable);
- Randomization strata of T2DM status (T2DM patients, non-T2DM patients);
- Randomization strata of NASH CRN fibrosis scoring system (F1, F2/F3);
- Baseline LFC (%) (<median, ≥ median);
- Baseline LFC (%);
- Baseline ALT (U/L);
- Baseline HbA1c (%);
- Baseline FPG (mmol/L);
- Previously diagnosed with type 2 diabetes mellitus (Yes, No);
- Diabetes duration (Years);
- Patient currently treated for diabetes (Yes, No);
- Alcohol status (Never, former, current);
- If former or current, alcohol units consumed per week;
- Habitual cigarette smoking status (Never, former, current);
- If former or current, number of cigarettes per day;
- Other habitual tobacco or nicotine use (Never, former, current);
- Any history of drug abuse (Yes, No);
- Site pooling (Investigators speciality [Hepatologist, Others]);

The demographic and baseline characteristics table will be repeated in 4 additional populations in the ITTS: Diabetic patients, non-diabetic patients, F1 patients and F2/F3 patients. All of these populations will be based on the randomization strata. The derivation of the medians for BMI and LFC will be based on the subset populations.

For randomization strata, the stratification factors as used in the IWRS randomization will be summarized.

No formal tests of statistical significance will be performed on the demographic and baseline data.

Other baseline measurements, such as vital signs and ECG, will be summarized by treatment group with post-baseline measurements.

Demographic and baseline characteristics table will also be repeated in ITTS-w-065-S

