7.6.2.5 Subgroup Analysis

Analysis of responder defined as relative reduction in LFC $\geq 30\%$ from baseline to Week 36 (V8-EoT), will have a subgroup analysis performed using multiple imputation as per Section 7.6.1.1 for the following groups:

- Randomization strata of T2DM status (T2DM patients, non-T2DM patients)
- Randomization strata of NASH CRN fibrosis scoring system (F1, F2/F3)

The MMRM analysis described in Section 7.6.2.3 will have subgroup analysis performed for the following parameters and subgroups in the ITT Set:

- ALT (U/L)
 - Randomization strata of T2DM status (T2DM patients, non-T2DM patients)
 - Randomization strata of NASH CRN fibrosis scoring system (F1, F2/F3)
- AST (U/L)
 - Randomization strata of T2DM status (T2DM patients, non-T2DM patients)
 - Randomization strata of NASH CRN fibrosis scoring system (F1, F2/F3)
- FPG (mmol/L)
 - Randomization strata of T2DM status (T2DM patients, non-T2DM patients)
- HbA1c (%)
 - Randomization strata of T2DM status (T2DM patients, non-T2DM patients)

Statistical Analysis Plan

Sponsor Name: Poxel
Sponsor Protocol ID: PXL065-003

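### The T2DM and fibrosis subgroups are formed from the IWRS randomization stratum, so any mis-stratified patient stays in the wrong disease subgroup in the ITTS

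*SAP*

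**What the plan says.** Protocol 9.5.1 lists among the primary-endpoint subgroups "T2DM status (T2DM patients versus non-T2DM patients") and "NASH CRN fibrosis scoring system (F1 versus F2/F3"). It does not say whether the value comes from clinical data or from the IWRS. The primary-analysis paragraph of the same section uses the same words for the stratification factors: "stratification factors, i.e. T2DM status (T2DM patients versus non-T2DM patients").

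The SAP settles the source:

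- 7.6.1.4 (primary endpoint, ITTS) uses "Randomization strata of T2DM status (T2DM patients, non-T2DM patients") and the corresponding fibrosis stratum, with an interaction test at 0.10.
- 7.6.2.5 (30% LFC responder, ALT, AST, FPG, HbA1c) uses the same strata, for example "Randomization strata of NASH CRN fibrosis scoring system (F1, F2/F3"). FPG and HbA1c are split by T2DM only.
- 7.4 repeats the baseline table in diabetic, non-diabetic, F1 and F2/F3 patients and adds: "All of these populations will be based on the randomization strata". It also explains that randomization strata means the factors as used in the IWRS.

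Two other places treat actual status as a separate variable. SAP 7.2 plans a table and listing of "discrepancies between the stratification factors in the database and Interactive Web Response System (IWRS"). SAP 5.9 states: "Patients in the PPS will be analyzed based on treatment actually received and actual strata rather than randomized".

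**The concern.** The stratum as randomized is the natural covariate in an ITTS model. A subgroup analysis asks something else: whether patients with and without diabetes, or with F1 and with F2/F3, respond differently. That calls for disease status. If the IWRS entry was wrong, the stratum records the error and not the disease.

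The other patient-level subgroups in 7.6.1.4 (age, BMI, sex, baseline LFC) use patient characteristics; only these two use an allocation record. The 7.2 table would reveal a misfiled patient, but no planned ITTS subgroup result would move that patient to the right group. In 7.4, a known diabetic misfiled as non-T2DM would appear in the non-diabetic table while counted there as previously diagnosed.

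The trial recruits both populations on purpose (Protocol 4.1: at least 50% T2DM, at most 35% F1). At stake is how accurately it can describe consistency of effect across them. The overall treatment comparison is not affected.

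**Working it through.** **The plan's own figure.** Protocol 9.2 assumes a difference of 30, SD 30, one-sided 0.025 and 90% power. The normal formula gives 2 × (1.960 + 1.282)² × (30/30)² ≈ 21.0, so 22 per arm. With the t distribution, 22 per arm has 89.97% power and 23 has 91.2%. The stated 23 reproduces. The synopsis uses 24 evaluable per arm: 24/0.8 = 30 randomized.

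**Attenuation formula.** Let p be the true share with the feature and e the probability of being filed in the wrong stratum, the same in both directions and unrelated to treatment. Then:

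- share filed as having the feature: a = p(1 − e) + (1 − p)e
- PPV = p(1 − e)/a, the fraction filed as having the feature who truly have it
- NPV = (1 − p)(1 − e)/(1 − a), the same for those filed as not having it
- expected observed interaction = true interaction × (PPV + NPV − 1)

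**Inputs.** p = 0.50 for T2DM (the minimum share) and 0.35 for F1 (the cap). The documents give no e, so 1% to 10% is assumed, about 1 to 12 of 120 patients.

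**Worked case, e = 5%.**

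- T2DM: a = 0.50 and PPV = NPV = 0.95, so the factor is 0.90.
- F1: a = 0.3325 + 0.0325 = 0.365; PPV = 0.3325/0.365 = 0.911; NPV = 0.6175/0.635 = 0.972. The factor is 0.883.

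A simulation with these inputs gave 0.900 and 0.884.

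**Power.** For one dose against placebo at 24 per arm, SE = 30 × √(2/n₁ + 2/n₂), where n₁ and n₂ are the patients per arm in the two subgroups. The normal approximation is used with a two-sided 0.10 test and an assumed true interaction of 30 points. With no errors, the T2DM SE is 30 × √(2/12 + 2/12) = 17.3 and the F1 SE is 30 × √(2/8.4 + 2/15.6) = 18.2.

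| Assumed error rate | T2DM: share kept | T2DM: power | F1: share kept | F1: power |
|---|---|---|---|---|
| 0 | 1.00 | 53.5% | 1.00 | 50.3% |
| 1% | 0.98 | 52.1% | 0.98 | 48.9% |
| 2% | 0.96 | 50.8% | 0.95 | 47.5% |
| 5% | 0.90 | 46.6% | 0.88 | 43.3% |
| 10% | 0.80 | 39.9% | 0.77 | 36.6% |

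Errors in one direction only do less harm. At 5% the T2DM factor is 0.95. The F1 factor is 0.97 if F1 patients are filed as F2/F3, and 0.92 (0.915) if F2/F3 patients are filed as F1.

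**The case against.** A reader might infer that the protocol defines these subgroups by clinical status and that the SAP overrides it. The text does not support this: Protocol 9.5.1 names no source and uses the same phrase for the stratification factors, so the SAP clarifies an open point. Nor does the absence of an entry in SAP Section 8 show an unlogged change. That section lists changes between SAP versions, and nothing shows that a previous version classified these patients differently.

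A reader might also take the interactions to be biased toward zero as a matter of fact. That requires errors to exist, to be unrelated to treatment, and a true interaction to be present. There are controls at entry: Protocol 8.2.2 makes the central biopsy report source data for eligibility, and Protocol 7.2.1 has the biopsy criteria reviewed at the randomization visit.

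One misfiled patient is about 7% of a non-T2DM arm (1/15) or 10% of an F1 arm (1/10.5), but this does not correspond to the 5-10% rows above. A rate of 1 in 15 across both T2DM strata and all four arms means 8 errors in 120. A single error can weigh on the one dose contrast it falls in, but across the trial it is near the 1% row.

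Further points stand. The interaction test is specified only for the primary endpoint; 7.6.2.5 specifies none. Sample size limits the test more than filing errors do: power is only 50-54% with perfect classification. The PPS pairs actual strata with actual treatment, a coherent as-treated convention, and randomized strata in the ITTS are coherent too. Finally, the trial is for internal decision and the subgroups are a consistency check.

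What the objection does not remove is that the SAP allows for discrepancies and plans no ITTS subgroup result that corrects them.

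**Conclusion.** The point holds as a low-severity, free improvement. The SAP classifies the two disease subgroups by allocation record, so any mis-stratified patient is in the wrong subgroup throughout the ITTS subgroup analyses and the 7.4 subset tables.

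The expected loss of a true subgroup difference is about 2% at a 1% error rate, 10-12% at 5% and 20-23% at 10%, and zero without errors. These figures rest on assumed error rates, symmetric errors unrelated to treatment, and subgroup shares at the protocol's limits. The power figures also assume a 30-point interaction and 24 evaluable patients per arm. They apply to the primary-endpoint interaction test. For the secondary subgroups the effect would be some mixing of the two groups' estimates. The primary ANCOVA result is not in question.

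**What to change.** In SAP 7.6.1.4, 7.6.2.5 and the subset tables of 7.4, define T2DM status from the eCRF diabetes history and F1 versus F2/F3 from the central read of the baseline biopsy. At minimum, pre-specify that these analyses are repeated on actual status if the 7.2 discrepancy table is not empty.

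Keep the randomization strata as ANCOVA and MMRM covariates and as CMH strata in the ITTS. State whether the matching stratum covariate is dropped when actual status enters a subgroup model, since the two columns are identical if there are no discrepancies.

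The choice should be fixed before unblinding; made afterwards, it should be reported as post hoc. The cost is a few lines of SAP text and a changed subgroup variable. No new data are needed, because both versions are already to be compared under 7.2.

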7.6 Efficacy

7.6.1 Primary Endpoint

7.6.1.1 Primary Analysis

The primary evaluation of efficacy will be based on MRI-PDFF. The primary endpoint will be the relative change in the percentage of LFC from baseline to Week 36 (V8-EoT) in the ITTS.

For patients who withdraw from the study at or after Week 12 (V4), the LFC will be assessed at ET as far as possible. With the assumption that the LFC assessed at or after Week 12 (V4) reflects what could have been observed at Week 36 (V8-EoT), the missing LFCs at Week 36 (V8-EoT) will be estimated by this value. For patients who withdraw before Week 12 (V4) or withdraw without any LFC assessment at or after Week 12 (V4), LFC missing values at Week 36 (V8-EoT) will be imputed using a multivariate imputation approach by fully conditional specification (FCS) regression method assuming missing at random (MAR) mechanism. The set of variables included in the multiple imputation model will be randomized treatment, type 2 diabetes mellitus status (T2DM patients versus non-T2DM patients), NASH CRN fibrosis scoring system (F1 versus F2/F3), and baseline LFC. The number of imputed datasets generated will be 1000 with the burn-out iterations set at 100. A minimum value of 0 and a maximum value of 50 will also be applied to restrict imputed LFC values, see

Statistical Analysis Plan

Sponsor Name: Poxel
Sponsor Protocol ID: PXL065-003

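### If the subgroup analyses use the listed imputation model, treatment-by-subgroup differences shrink toward zero roughly in proportion to the imputed share, and the 0.10-level interaction test becomes conservative

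*SAP*

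**What the plan says.** **Subgroup analysis of the primary endpoint (SAP 7.6.1.4).** There are seven subgroups: age, BMI, sex, T2DM stratum, fibrosis stratum, baseline LFC and site pooling. Differences in LS means are shown with 90% intervals. "The subgroup by treatment interaction will be tested at the nominal alpha level of 0.1." The analysis set is given ("The subgroup analysis will be performed on the ITTS"), but nothing is said about missing Week 36 values.

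**Imputation model (SAP 7.6.1.1).** "The set of variables included in the multiple imputation model will be randomized treatment, type 2 diabetes mellitus status", followed by "NASH CRN fibrosis scoring system (F1 versus F2/F3), and baseline LFC". No product term is mentioned. Imputed values are bounded: "A minimum value of 0 and a maximum value of 50 will also be applied to restrict imputed LFC values".

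**Who is imputed (SAP 7.6.1.1).** A withdrawal with a scan at or after Week 12 is not multiply imputed: "the missing LFCs at Week 36 (V8-EoT) will be estimated by this value". Multiple imputation is for the rest: "For patients who withdraw before Week 12 (V4) or withdraw without any LFC assessment at or after Week 12 (V4), LFC missing values".

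**Responder subgroups (SAP 7.6.2.5).** The analysis of the 30% relative-reduction responder by T2DM and fibrosis stratum "will have a subgroup analysis performed using multiple imputation as per Section 7.6.1.1". No interaction test is specified there.

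**Analyses without imputation.** SAP 7.6.1.3 repeats 7.6.1.1 and 7.6.1.2 without multiple imputation; 7.6.1.4 is not included. SAP 7.6.2.2 gives the responder analyses a version without imputation, but 7.6.2.5 names only multiple imputation for their subgroups.

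**The concern.** Protocol 9.5.1 gives the purpose of the forest plot and interaction tests: to see whether the treatment effect is consistent across subgroups. If missing outcomes are drawn from a model with one common treatment effect, the imputed patients show consistency by construction, whatever the truth. Mixing them with observed patients dilutes any real difference. Rubin's rules then attach a standard error that is too large for the diluted estimate, so the test rejects less often than its nominal level.

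The trial is meant to inform dose choice for Phase 3 in a mixed T2DM and non-T2DM population (Protocol 4.2). A consistency check tilted toward agreement is therefore unhelpful, and the plan specifies no subgroup result free of the assumption.

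**Working it through.** **1. The plan's own figure.** Inputs from SAP 2.3: difference 30, SD 30, two-sided alpha 0.05, power 90%. The normal approximation gives n = 2 × (1.960 + 1.282)² × (30/30)² = 21.0, rounded up to 22 per arm. With the noncentral t, power is 0.8997 at 22 and 0.912 at 23, so the stated 23 is reproduced. Dropout: 23/0.8 = 28.75, or 29; 24/0.8 = 30. The SAP says around 30.

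**2. Expected attenuation.** Let m be the share imputed and δ the true interaction. Observed patients carry δ and imputed patients carry none, so the estimate is about (1 − m) × δ. For δ = −30 this gives −28.5, −27, −25.5 and −24 at m = 5%, 10%, 15% and 20%. With 30 per arm, 5%, 10% and 20% are 1.5, 3 and 6 patients per arm.

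**3. Expected effect on the test at m = 20%.** With 24 observed per arm split 12/12, the observed-data standard error of a one-dose interaction is 30 × √(4/12) = 17.3. Power at two-sided 0.10 is Φ(30/17.3 − 1.645) = 0.535. Under imputation without the product term the true sampling spread shrinks to about 0.8 × 17.3 = 13.9. The simulated values were 14 points for the spread and 19 for the Rubin standard error. The critical value is then 1.645 × 19 = 31.3, so power is 1 − Φ((31.3 − 24)/14) = 0.30, and rejection under no interaction is 2 × (1 − Φ(31.3/14)) = 0.03 rather than 0.10.

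**4. Simulation.** Four arms of 30, SD 30, true interaction of 30 points in all doses, 2,500 trials per row (Monte Carlo error about 0.01). Imputation was bounded 0 to 50, with 40 imputations instead of the planned 1000. Assumed, because the documents do not give them: 50/50 subgroup, data missing completely at random, baseline LFC mean 20 and SD 6. Each power cell shows listed model / observed data / listed model plus subgroup and product.

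| Imputed | Mean estimate, listed model | Power, one dose vs placebo (1 df) | Power, all doses (3 df) |
|---|---|---|---|
| 5% | −28.3 | 0.53 / 0.59 / 0.57 | 0.51 / 0.58 / 0.58 |
| 10% | −25.9 | 0.43 / 0.54 / 0.51 | 0.37 / 0.52 / 0.50 |
| 15% | −25.0 | 0.37 / 0.53 / 0.49 | 0.28 / 0.51 / 0.47 |
| 20% | −23.0 | 0.28 / 0.49 / 0.45 | 0.19 / 0.48 / 0.42 |

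With no missing data the mean was −29.0 to −29.8. Repeat simulations differ by a few hundredths in power; the rounded figures in the verdict take them together.

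**5. No true interaction.** Rejection at nominal 0.10 was about 0.07, 0.06 and 0.03 (1 df), and about 0.08, 0.05 and 0.01 to 0.02 (3 df), at 5%, 10% and 20% imputed.

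**6. Which omission matters.** At 20% imputed, adding only the subgroup main effect left 3-df power at 0.18 either way (mean −22.5 with it, −23.2 without). Adding the product restored the mean to −28.6.

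**The case against.** - **7.6.1.4 does not say imputed data are used.** Where the SAP carries the imputation to another analysis (7.6.2.1, 7.6.2.2, 7.6.2.5) it says so. A reader might infer that the interactions are certainly tested on imputed data; the text does not establish that. It remains the natural reading for the primary endpoint on the ITTS, and the silence itself needs resolving.
- **The form of the imputation model cannot be seen.** 7.6.1.1 lists variables, not terms, and the Appendix B code is blacked out. A reader might infer a main-effects-only model. For T2DM, fibrosis and baseline LFC that cannot be confirmed. For age, BMI, sex and site pooling the variables are not listed, so no product with them can be in the model as described.
- **The imputed share is probably below 20%.** Early-termination scans at or after Week 12 replace imputation, and 20% is total dropout. This stands. Some imputation is still likely, because withdrawals before Week 12 have no such scan and patients lost to follow-up have no termination visit.
- **Power is low anyway.** A 30-point interaction equals the whole design effect, and power without missing data is only about 0.6. Low power is mainly a matter of sample size, which no imputation change cures. The further loss is avoidable.
- **The stakes are limited.** This is a Phase 2 trial for internal decisions, no decision rule hangs on the interaction tests, and the error is conservative. That makes the point modest but does not remove it.

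**Conclusion.** The point holds conditionally. If the imputation of 7.6.1.1 feeds the subgroup analyses without treatment-by-subgroup products, differences between subgroups shrink roughly by the imputed share and the 0.10-level test is conservative. For a true 30-point interaction the mean estimate is about −28, −26 to −27 and −23 to −24 at 5%, 10% and 20% imputed. One-degree-of-freedom power is about 0.52, 0.44 and 0.30, against 0.58, 0.53 and 0.50 on observed data: relative losses of about 10%, 17% and 40%. These figures rest on the simulation assumptions above and on 30 per arm before the site exclusion in SAP section 5.

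Three stronger readings are not supported. A large loss of power cannot be asserted, because the documents do not give the imputed share and at 5% the loss is small. The absence of age, BMI, sex and site pooling as main effects is not what does the damage; the missing product term is. The power figures do not carry over to 7.6.2.5, which plans no interaction test; the concern there is that differences between T2DM or fibrosis strata in the responder analysis are attenuated.

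**What to change.** In SAP 7.6.1.4, state how missing Week 36 LFC is handled, and choose one of two routes.

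1. Run the subgroup estimates and interaction tests on non-imputed Week 36 data, keeping the rule that a scan at or after Week 12 stands in for Week 36. Little is lost: only the outcome is imputed, and the listed imputation variables are the same as the ANCOVA covariates, so imputation adds no information to that model.
2. For each subgroup's analysis, add the subgroup variable and its product with treatment to the FCS model.

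In SAP 7.6.2.5, do the same for the T2DM and fibrosis responder subgroups.

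The cost is SAP wording and, under the second route, extra imputation runs. Intervals will be wider in small subgroup-by-arm cells. Subgroup-specific imputation also means that rows of the forest plot no longer share the primary analysis's imputed data, which a footnote should say. At 20% imputed, 1-df power was 0.49 under the first route and 0.45 under the second, against 0.28 with the listed model.
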